6.3.2 Imaging

Immune Related Response Criteria

Because of direct clinical observations of immune cell influx into tumor causing enlargement in some patients prior to sustained response, recently it has been suggested that clinical trials involving the use of immunotherapy use alternative guidelines, called immune related response criteria (irRC) to determine radiographic response or progression after therapy²². These recommendations have been used in recent clinical trials. One study of 227 subjects with metastatic melanoma showed that the approximately 10% of patients who had PD by modified WHO criteria but either of CR, PR or SD by irRC had a similar overall survival as those patients who had SD, PR or CR by both criteria. The irRC was created using bidimensional measurements (as previously widely used in the WHO criteria). We have taken the concepts of the irRC and combined them with the recently revised RECIST 1.1²³ to come up with the modified irRC used in this protocol. Consistent with the irRC, the main changes from RECIST 1.1 are (a) a requirement for confirmation of both progression and response by imaging at least 4 weeks after initial imaging and (b) not automatically calling the appearance of new lesions progressive disease if the total measurable tumor burden has not met criteria for progressive disease.

For immune-related response criteria (irRC), only index and measurable new lesions are taken into account. At baseline tumor assessment on this trial, target lesions will be measured along the longest axis and the measurements will be summed, called sum of largest diameter (SLD). These lesions must be a minimum of 10mm per lesion, maximum of 5 target lesions, maximum of 2 per organ system. At each subsequent tumor assessment, the unidimensional measurement of target lesions and of new measureable lesions are added together to provide the total tumor burden: As per the modified definitions below, all responses and progression except stable

disease (SD) require confirmation on a consecutive scan at least 4 weeks from the initial observation).

Definitions of irRC:

Response	irRC
New measurable lesions	Incorporated into tumor burden
New non-measurable lesions	Do not define progression (but precludes irCR)
Non-index lesions	Contributes to defining irCR (complete disappearance required)
Overall irCR	100% disappearance of all lesions, whether measurable or not, and no new lesions, in two consecutive observations not less than 4 wks from the date first documented. All measurable lymph nodes also must have reduction in short axis to <10mm.
Overall irPR	≥ 30% decrease in SLD compared with baseline confirmed by a consecutive assessment at least 4 wk after first documentation
Overall irSD	Not meeting criteria for irCR or irPR, in absence of irPD: 30% decrease in SLD compared with baseline cannot be established nor 20% increase compared with nadir.
Overall irPD	At least 20% increase in SLD compared with nadir (minimum recorded tumor burden) and an increase of at least 5mm over the nadir, confirmed by a repeat, consecutive observations at least 4 wk from the date first documented.

Overall responses derived from changes in index, non-index and new lesions as demonstrated in the following table:

Measurable response	Non-measurable response		Overall response using irRC
	Non-index lesions	New, non-measurable lesions	
Index and new, measurable lesions (tumor burden)* %			
Decrease 100	Absent	Absent	irCR ^{&}
Decrease 100	Stable	Any	irPR ^{&}
Decrease 100	Unequivocal progression	Any	irPR ^{&}
Decrease ≥ 30%	Absent / Stable	Any	irPR ^{&}
Decrease ≥ 30%	Unequivocal progression	Any	irPR ^{&}

Decrease < 30 to increase < 20	Absent / Stable	Any	irSD
Decrease < 30 to increase < 20	Unequivocal progression	Any	irSD
Increase ≥ 20	Any	Any	irPD

* Decreases assessed relative to baseline

& Assuming response (irCR) and progression (irPD) are confirmed by a second, consecutive assessment at least 4 weeks apart.

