2 ELIGIBILITY ASSESSMENT AND ENROLLMENT

2.1 Eligibility Criteria

2.1.1 Inclusion Criteria

- 2.1.1.1 Diagnosis: Patients must have histologically confirmed medullary thyroid cancer by the Laboratory of Pathology or a pathology report and history consistent with medullary thyroid cancer. It is not uncommon for a secondary, minor pathologic focus of another form of thyroid cancer to be coincidentally found in 15-20% of patients with medullary thyroid cancer²¹. In such cases, eligibility is based on the discretion of the investigator.
- 2.1.1.2 Patients must have evidence of metastatic medullary thyroid cancer including disease that is evaluable on bone, CT scan or MRI. (Patients who are surgical candidates and potentially rendered disease free with surgical resection are not eligible.)
- 2.1.1.3 Patients must have elevated calcitonin levels greater than 40 pg/mL
- 2.1.1.4 Patients must have minimal or no disease related-symptoms (Minimal symptoms will include those that do not affect activities of daily living or pain that does not require regularly scheduled narcotics.)
- 2.1.1.5 Patients must have evaluable disease on imaging
- 2.1.1.6 No history of seizures, encephalitis, or multiple sclerosis.
- 2.1.1.7 Age \geq 18 years
- 2.1.1.8 ECOG performance status of 0-1 at study entry (Karnofsky \geq 70) (See [Appendix A](#)).
- 2.1.1.9 Female subject of childbearing potential should have a negative urine or serum pregnancy within 72 hours prior to receiving the first dose of study medication. If the urine test is positive or cannot be confirmed as negative, a serum pregnancy test will be required.
- 2.1.1.10 Female subjects of childbearing potential must be willing to use an adequate method of contraception as outlined in Section [10.6](#), Contraception, for the course of the study through 120 days after the last dose of study medication.
Note: Abstinence is acceptable if this is the usual lifestyle and preferred contraception for the subject
- 2.1.1.11 Male subjects of childbearing potential must agree to use an adequate method of contraception as outlined in Section [10.6](#), Contraception, starting with the first dose of study therapy through 120 days after the last dose of study therapy.
Note: Abstinence is acceptable if this is the usual lifestyle and preferred contraception for the subject
- 2.1.1.12 Willing to travel to the NIH for follow-up visits
- 2.1.1.13 Able to understand and sign informed consent.

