6.3 Response Criteria

For the purposes of this study, patients should be re-evaluated for response per the study calendar (3.4). In addition to a baseline scan, confirmatory scans should also be obtained not less than 4 weeks following initial documentation of objective response.

Responses will be assessed using both serum calcitonin levels and imaging using Immune Related Response Criteria below.

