6.3.3 Disease Parameters

Evaluable disease: Disease that can be evaluated on imaging but does not meet the measurable disease criteria below.

Measurable disease: Measurable lesions are defined as those that can be accurately measured in at least one dimension (longest diameter to be recorded):

- By chest x-ray: ≥20 mm;
- By CT scan:
 - Scan slice thickness 5 mm or under: as ≥10 mm
 - Scan slice thickness >5 mm: double the slice thickness

With calipers on clinical exam: ≥10 mm. Malignant lymph nodes. To be considered pathologically enlarged and measurable, a lymph node must be ≥15 mm in short axis when assessed by CT scan (CT scan slice thickness recommended to be no greater than 5 mm). At baseline and in follow-up, only the short axis will be measured and followed.

Non-measurable disease. All other lesions (or sites of disease), including small lesions (longest diameter <10 mm or pathological lymph nodes with ≥10 to <15 mm short axis), are considered non-measurable disease. Bone lesions, leptomeningeal disease, ascites, pleural/pericardial effusions, lymphangitis cutis/pulmonitis, inflammatory breast disease, and abdominal masses (not followed by CT or MRI), are considered as non-measurable.

Note: Cystic lesions that meet the criteria for radiographically defined simple cysts should not be considered as malignant lesions (neither measurable nor non-measurable) since they are, by definition, simple cysts.

‘Cystic lesions’ thought to represent cystic metastases can be considered as measurable lesions, if they meet the definition of measurability described above. However, if non-cystic lesions are present in the same patient, these are preferred for selection as target lesions.

Target lesions. All measurable lesions up to a maximum of 2 lesions per organ and 5 lesions in total, representative of all involved organs, should be identified as **target lesions** and recorded and measured at baseline. Target lesions should be selected on the basis of their size (lesions with the longest diameter), be representative of all involved organs, but in addition should be those that lend themselves to reproducible repeated measurements. It may be the case that, on

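### Patients with no target lesion may enrol, but section 6.3.2 cannot score partial response or growth of existing disease in them; if PFS uses 6.3.2, it can only be too long in these patients.

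*Combined protocol and SAP*

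**What the plan says.** **Who may enrol.** Section 2.1.1 requires metastatic disease, "including disease that is evaluable on bone, CT scan or MRI", and adds: "Patients must have evaluable disease on imaging". Measurable disease is not required. Section 6.3.3 defines evaluable disease as "Disease that can be evaluated on imaging but does not meet the measurable disease criteria below". It draws target lesions only from measurable lesions. Its list of non-measurable disease includes "Bone lesions, leptomeningeal disease, ascites, pleural/pericardial effusions", as well as small lesions and small nodes.

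**How imaging is scored.** Section 6.3 says: "Responses will be assessed using both serum calcitonin levels and imaging using Immune Related Response Criteria below". Section 6.3.2 introduces these criteria as a way "to determine radiographic response or progression after therapy" and then states: "For immune-related response criteria (irRC), only index and measurable new lesions are taken into account". Partial response (irPR) is a confirmed fall in SLD of at least 30% from baseline. Progression (irPD) is a confirmed rise of at least 20% and at least 5 mm over the nadir. Non-index lesions count only toward complete response (irCR), and new non-measurable lesions do not define progression. One stated departure from RECIST 1.1 is "not automatically calling the appearance of new lesions progressive disease if the total measurable tumor burden has not met criteria for progressive disease".

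**PFS.** Section 1.1.2 makes PFS a secondary objective. Section 6.3.6 runs it from start of treatment to progression or death and names no criterion for progression. Section 3.5.1 ends therapy for progression by symptoms or by the criteria in 6.3.2, but does not say that either is a PFS event.

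**The concern.** The eligibility rule and the scoring rule do not fit together. The immune-related criteria deliberately stop new or non-index lesions from defining progression on their own, to avoid calling pseudo-progression. That is reasonable when there is a measurable burden that can show true progression instead. A patient with no target lesion has no such burden at baseline, so the safeguard removes the imaging route to progression for all the disease the patient entered with.

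What is at stake is the secondary PFS estimate and its description by cohort. Cohorts are formed by vaccine history (section 2.4), so nothing balances the number of such patients between them. The imaging response fraction is touched as well, because its denominator may include patients who cannot reach partial response.

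**Working it through.** **Inputs.** Section 8: 15 evaluable patients per cohort, cut-off 4, true rates 10% and 40%. Section 6.3.2: the irPR and irPD thresholds above. Sections 3.1 and 3.4: 2 years of treatment, imaging every 3 months. Not given: k, the number of patients with no target lesion, and m, the number of these who are alive at a landmark and whose only progression so far is unscorable.

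**1. The plan's own figures.** P(X ≥ 4) = 1 − Σ C(15,i) pⁱ(1−p)¹⁵⁻ⁱ for i = 0 to 3.
- p = 0.10: 1 − (0.2059 + 0.3432 + 0.2669 + 0.1285) = 0.0556. The plan says 5.6%.
- p = 0.40: 1 − (0.0005 + 0.0047 + 0.0219 + 0.0634) = 0.9095. The plan says 90.9%.

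Both reproduce. Every patient enters with calcitonin above 40 pg/mL and can qualify for the primary composite by calcitonin.

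**2. Section 6.3.2 applied to a patient with baseline SLD = 0.**

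| Event | Effect on SLD | Result |
|---|---|---|
| Existing lesions shrink but persist | stays 0; 30% fall is 0/0 | irPR impossible |
| All lesions disappear, confirmed | not needed | irCR possible |
| Existing lesions grow unequivocally | stays 0 | cannot be irPD |
| New bone or other non-measurable lesion | stays 0 | cannot be irPD |
| New measurable lesion | 0 to at least 10 mm | scorable: clears 5 mm; the percentage is only formally undefined |

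No row of the overall-response table covers a patient without index lesions. Its nearest rows, where measurable burden changes by less than the thresholds, give stable disease even with unequivocal non-index progression. Over 24/3 = 8 scheduled assessments, none can return irPD for the third or fourth event.

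**3. Direction for PFS.** If 6.3.2 supplies the progression event, leaving out true progressions can lengthen PFS or leave it unchanged. It cannot shorten it.

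**4. Size.** With complete follow-up to a landmark, the overstatement in a cohort of 15 is m/15:
- m = 0: 0 points
- m = 1: 1/15 = 6.7 points
- m = 2: 2/15 = 13.3 points
- m = 3: 3/15 = 20.0 points

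**5. Could the case arise?** This needs an assumed share f of patients with no target lesion. P(at least one in 15) = 1 − (1−f)¹⁵, which is 54%, 79% and 96% at f = 5%, 10% and 20%. These figures concern enrolment, not missed events. If a quarter of such patients had only unscorable progression by the landmark (also assumed), P(m ≥ 1) = 1 − (1 − f/4)¹⁵ = 17%, 32% and 54%.

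k also depends on a definition. Section 6.3.2 asks for at least 10 mm on the longest axis, and 6.3.3 asks for nodes of at least 15 mm in short axis. A node of 12 mm in short axis meets the first and not the second.

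**6. Response fraction (illustration).** Two responders are 2/15 = 13% (exact 95% CI 1.7 to 40.5%) over all patients, or 2/12 = 17% (2.1 to 48.4%) if 3 have no target lesion.

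**The case against.** **PFS may not use 6.3.2.** Section 6.3.6 names no criterion, so a flat statement that PFS is biased long would go beyond the text. This stands, and the conclusion is conditional. Section 6.3.2 is still the evident imaging standard: it says it serves progression as well as response, and 3.5.1 refers to it for progression. If symptomatic progression counts, some of the missed events are recovered.

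**The scoring is deliberate.** Also true, and for patients with target lesions it should be left alone. A reader might infer that the non-index rule should be applied to everyone so that the cohorts share one definition. The documents do not support making that the main analysis, because it would reverse the protocol's chosen progression concept where that concept works.

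**Imaging progression is not lost altogether.** A reader might infer that these patients can never progress on imaging. They can, through a new measurable lesion.

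**The size is unknown.** This stands. m/15 is an identity, the plan sets no PFS landmark, and the shares in step 5 have no basis in the documents.

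**The consequence is limited.** PFS has no threshold or test attached, and section 8 disclaims power for a formal comparison of the cohorts. This stands too.

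Dating of the event and loss of the confirming scan affect every patient. They are separate drafting matters and lend this point no weight.

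**Conclusion.** The concern holds in conditional form. Patients with no target lesion are eligible. A stated rule, not merely a missing detail, makes irPR impossible in them and leaves growth of existing disease and new bone lesions outside irPD. If PFS uses 6.3.2, it can only be too long in these patients, less so if symptomatic progression is an event.

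Each patient whose only progression is unscorable adds 6.7 percentage points to landmark PFS in a cohort of 15, assuming complete follow-up. The documents give neither m nor k, so no bias in months and no difference between cohorts can be claimed.

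A reader might infer that the primary analysis is compromised. It is not: the 4-of-15 rule reproduces, and the calcitonin route stays open to every patient. The effect is on secondary estimates and their description.

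**What to change.** For analysis only:

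1. In 6.3.6, name the modified irRC of 6.3.2 as the imaging criterion for PFS and state whether symptomatic progression is an event.
2. For patients with no baseline target lesion, count as progression unequivocal non-index progression or unequivocal new lesions, confirmed on a consecutive scan at least 4 weeks later. The next 3-monthly scan suffices.
3. Keep 6.3.2 as written for patients with target lesions. Applying the rule in item 2 to all patients may be an optional sensitivity analysis, no more.
4. Report by cohort the number with no target lesion, and give the imaging response fraction with its denominators. Any irCR in a patient without a target lesion belongs in the all-patient fraction.
5. Reconcile the effusion and FDG-PET text in 6.3.4, which lets a new or worsening effusion or a new PET lesion indicate progression, with 6.3.2.

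Eligibility, the primary composite and the criteria for removal from therapy stay unchanged.

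**Cost.** Wording in 6.3.6 and section 8, and one table column. No new scans are needed: CT or MRI and bone scan are already 3-monthly (section 3.4), and unequivocal progression of non-target lesions is already to be noted (section 6.3.3). The downside is somewhat shorter PFS and a less quantitative progression call in a few patients. The rule should be set before PFS is analysed, so that the choice is not driven by the data.

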6.3.3 Disease Parameters

Evaluable disease: Disease that can be evaluated on imaging but does not meet the measurable disease criteria below.

Measurable disease: Measurable lesions are defined as those that can be accurately measured in at least one dimension (longest diameter to be recorded):

- By chest x-ray: ≥20 mm;
- By CT scan:
 - Scan slice thickness 5 mm or under: as ≥10 mm
 - Scan slice thickness >5 mm: double the slice thickness

With calipers on clinical exam: ≥10 mm. Malignant lymph nodes. To be considered pathologically enlarged and measurable, a lymph node must be ≥15 mm in short axis when assessed by CT scan (CT scan slice thickness recommended to be no greater than 5 mm). At baseline and in follow-up, only the short axis will be measured and followed.

Non-measurable disease. All other lesions (or sites of disease), including small lesions (longest diameter <10 mm or pathological lymph nodes with ≥10 to <15 mm short axis), are considered non-measurable disease. Bone lesions, leptomeningeal disease, ascites, pleural/pericardial effusions, lymphangitis cutis/pulmonitis, inflammatory breast disease, and abdominal masses (not followed by CT or MRI), are considered as non-measurable.

Note: Cystic lesions that meet the criteria for radiographically defined simple cysts should not be considered as malignant lesions (neither measurable nor non-measurable) since they are, by definition, simple cysts.

‘Cystic lesions’ thought to represent cystic metastases can be considered as measurable lesions, if they meet the definition of measurability described above. However, if non-cystic lesions are present in the same patient, these are preferred for selection as target lesions.

Target lesions. All measurable lesions up to a maximum of 2 lesions per organ and 5 lesions in total, representative of all involved organs, should be identified as **target lesions** and recorded and measured at baseline. Target lesions should be selected on the basis of their size (lesions with the longest diameter), be representative of all involved organs, but in addition should be those that lend themselves to reproducible repeated measurements. It may be the case that, on

occasion, the largest lesion does not lend itself to reproducible measurement in which circumstance the next largest lesion which can be measured reproducibly should be selected. A sum of the diameters (longest for non-nodal lesions, short axis for nodal lesions) for all target lesions will be calculated and reported as the baseline sum diameters. If lymph nodes are to be included in the sum, then only the short axis is added into the sum. The baseline sum diameters will be used as reference to further characterize any objective tumor regression in the measurable dimension of the disease.

Non-target lesions. All other lesions (or sites of disease) including any measurable lesions over and above the 5 target lesions should be identified as **non-target lesions** and should also be recorded at baseline. Measurements of these lesions are not required, but the presence, absence, or in rare cases unequivocal progression of each should be noted throughout follow-up.

6.3.4 Methods for Evaluation of Measurable Disease

All measurements should be taken and recorded in metric notation using a ruler or calipers. All baseline evaluations should be performed as closely as possible to the beginning of treatment and never more than 4 weeks before the beginning of the treatment.

The same method of assessment and the same technique should be used to characterize each identified and reported lesion at baseline and during follow-up. Imaging-based evaluation is preferred to evaluation by clinical examination unless the lesion(s) being followed cannot be imaged but are assessable by clinical exam.

Clinical lesions: Clinical lesions will only be considered measurable when they are superficial (e.g., skin nodules and palpable lymph nodes) and ≥ 10 mm diameter as assessed using calipers (e.g., skin nodules). In the case of skin lesions, documentation by color photography, including a ruler to estimate the size of the lesion, is recommended.

Chest x-ray: Lesions on chest x-ray are acceptable as measurable lesions when they are clearly defined and surrounded by aerated lung. However, CT is preferable.

Conventional CT and MRI: This guideline has defined measurability of lesions on CT scan based on the assumption that CT slice thickness is 5 mm or less. If CT scans have slice thickness greater than 5 mm, the minimum size for a measurable lesion should be twice the slice thickness. MRI is also acceptable in certain situations (e.g. for body scans).

Use of MRI remains a complex issue. MRI has excellent contrast, spatial, and temporal resolution; however, there are many image acquisition variables involved in MRI, which greatly impact image quality, lesion conspicuity, and measurement. Furthermore, the availability of MRI is variable globally. As with CT, if an MRI is performed, the technical specifications of the scanning sequences used should be optimized for the evaluation of the type and site of disease. Furthermore, as with CT, the modality used at follow-up should be the same as was used at baseline and the lesions should be measured/assessed on the same pulse sequence. It is beyond the scope of the RECIST guidelines to prescribe specific MRI pulse sequence parameters for all scanners, body parts, and diseases. Ideally, the same type of scanner should be used and the image acquisition protocol should be followed as closely as possible to prior scans. Body scans should be performed with breath-hold scanning techniques, if possible.

PET-CT: At present, the low dose or attenuation correction CT portion of a combined PET-CT is not always of optimal diagnostic CT quality for use with RECIST measurements. However, if the site can document that the CT performed as part of a PET-CT is of identical diagnostic quality to a diagnostic CT (with IV and oral contrast), then the CT portion of the PET-CT can be used for RECIST measurements and can be used interchangeably with conventional CT in accurately measuring cancer lesions over time. Note, however, that the PET portion of the CT introduces additional data which may bias an investigator if it is not routinely or serially performed.

Ultrasound: Ultrasound is not useful in assessment of lesion size and should not be used as a method of measurement. Ultrasound examinations cannot be reproduced in their entirety for independent review at a later date and, because they are operator dependent, it cannot be guaranteed that the same technique and measurements will be taken from one assessment to the next. If new lesions are identified by ultrasound in the course of the study, confirmation by CT or MRI is advised. If there is concern about radiation exposure at CT, MRI may be used instead of CT in selected instances.

Endoscopy, Laparoscopy: The utilization of these techniques for objective tumor evaluation is not advised. However, such techniques may be useful to confirm complete pathological response when biopsies are obtained or to determine relapse in trials where recurrence following complete response (CR) or surgical resection is an endpoint.

Cytology, Histology: These techniques can be used to differentiate between partial responses (PR) and complete responses (CR) in rare cases (e.g., residual lesions in tumor types, such as germ cell tumors, where known residual benign tumors can remain).

The cytological confirmation of the neoplastic origin of any effusion that appears or worsens during treatment when the measurable tumor has met criteria for response or stable disease is mandatory to differentiate between response or stable disease (an effusion may be a side effect of the treatment) and progressive disease.

FDG-PET: While FDG-PET response assessments need additional study, it is sometimes reasonable to incorporate the use of FDG-PET scanning to complement CT scanning in assessment of progression (particularly possible 'new' disease). New lesions on the basis of FDG-PET imaging can be identified according to the following algorithm:

- a. Negative FDG-PET at baseline, with a positive FDG-PET at follow-up is a sign of PD based on a new lesion.
- b. No FDG-PET at baseline and a positive FDG-PET at follow-up: If the positive FDG-PET at follow-up corresponds to a new site of disease confirmed by CT, this is PD. If the positive FDG-PET at follow-up is not confirmed as a new site of disease on CT, additional follow-up CT scans are needed to determine if there is truly progression occurring at that site (if so, the date of PD will be the date of the initial abnormal FDG-PET scan). If the positive FDG-PET at follow-up corresponds to a pre-existing site of disease on CT that is not progressing on the basis of the anatomic images, this is not PD.
- c. FDG-PET may be used to upgrade a response to a CR in a manner similar to a biopsy in cases where a residual radiographic abnormality is thought to represent fibrosis or scarring. The use of FDG-PET in this circumstance should be prospectively

described in the protocol and supported by disease-specific medical literature for the indication. However, it must be acknowledged that both approaches may lead to false positive CR due to limitations of FDG-PET and biopsy resolution/sensitivity.

Note: A 'positive' FDG-PET scan lesion means one which is FDG avid with an uptake greater than twice that of the surrounding tissue on the attenuation corrected image.

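### FDG-PET item b in section 6.3.4 assigns progression without the tumour-burden threshold or 4-week confirmation that the modified irRC in 6.3.2 requires, and no text gives precedence for PFS and duration of response

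*Combined protocol and SAP*

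**What the plan says.** Section 6.3 names the imaging standard: "Responses will be assessed using both serum calcitonin levels and imaging using Immune Related Response Criteria below". Section 6.3.2 gives its two main departures from RECIST 1.1. The first is "a requirement for confirmation of both progression and response by imaging at least 4 weeks after initial imaging". The second is "not automatically calling the appearance of new lesions progressive disease if the total measurable tumor burden has not met criteria for progressive disease". In the definitions table, new measurable lesions are "Incorporated into tumor burden", and the entry for new non-measurable lesions reads "Do not define progression (but precludes irCR". irPD needs a rise over nadir of at least 20% and at least 5 mm, confirmed at 4 weeks or later.

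Section 6.3.4 then gives an FDG-PET algorithm and a cytology paragraph:

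- **Item a** (negative baseline PET): "Negative FDG-PET at baseline, with a positive FDG-PET at follow-up is a sign of PD based on a new lesion".
- **Item b** (no baseline PET): a positive PET at a new site that CT confirms is called PD outright. If CT does not confirm it, further CT follows, and if that shows progression at the site, PD takes the date of the first abnormal PET.
- **Item c**: "FDG-PET may be used to upgrade a response to a CR in a manner similar to a biopsy", on condition that this use is described prospectively in the protocol.
- **Cytology**: when measurable tumour is in response or stable, cytological confirmation of a new or worsening effusion is "mandatory to differentiate between response or stable disease (an effusion may be a side effect of the treatment) and progressive disease". Section 6.3.3 lists pleural and pericardial effusions as non-measurable disease.

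Sections 6.3.5 (duration of response) and 6.3.6 (PFS) refer to progression without naming a criterion. Section 3.5.1 ties removal from therapy to clinical progression or to irRC as described in 6.3.2. FDG-PET is not in the study calendar in 3.4.

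**The concern.** Section 6.3.2 is meant to stop a new lesion from being called progression on sight. Item b does exactly that once CT confirms the site. Item a and the cytology paragraph point the same way, less explicitly. A programmer or investigator deriving PFS from 6.3.6 finds no criterion there, and finds two sets of rules in the neighbouring sections that can give different answers for one patient.

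The patients exposed to this are not a random subset. PET is unscheduled and the trial is open label, so the stricter rule reaches only those whom someone chose to send for PET. Section 6.3.4 itself warns that PET information can bias an investigator when it is not obtained routinely.

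**Working it through.** No stated figure is in dispute, so the check compares the two rules and then applies both to the same findings.

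**Rules side by side**

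| | 6.3.2 (modified irRC) | 6.3.4, FDG-PET item b |
|---|---|---|
| New measurable lesion | added to the sum | PD if PET-positive and confirmed by CT |
| New non-measurable lesion | cannot define progression | PD if PET-positive and confirmed by CT |
| Size threshold | at least 20% and at least 5 mm over nadir | none |
| Repeat imaging | at least 4 weeks later | none once CT confirms the site |
| Date of PD | not stated in 6.3.2 | back to first abnormal PET where CT shows progression only later |

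**Applying both rules.** Take a new PET-positive, CT-visible lesion of 10 mm, no baseline PET, and all other lesions unchanged. The nadir sums are assumptions. The rise over nadir is 10 mm divided by the nadir sum, and 10 mm always passes the 5 mm test.

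- Nadir 30 mm: 10/30 = 33%. This reaches the irPD threshold but still needs confirmation. Item b: PD at once.
- Nadir 50 mm: 10/50 = 20%. Same result.
- Nadir 100 mm: 10/100 = 10%. Not irPD. Item b: PD.

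The rules therefore disagree on confirmation at every nadir, and on status itself once the nadir sum exceeds 10/0.20 = 50 mm.

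**Findings that add nothing to the sum.** A new non-nodal lesion of 8 mm on CT is below the 10 mm measurability limit in 6.3.3. It adds 0 mm, so it cannot produce irPD, yet item b calls it PD if PET-positive and confirmed by CT. An effusion also adds 0 mm. The cytology paragraph implies that a malignant one may be PD, although it does not say so outright.

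**Primary rule.** Section 8 gives 5.6% and 90.9% for 4 or more of 15 at true rates of 10% and 40%. Exact binomial tails are 0.0556 and 0.9095, so both reproduce. Neither depends on how progression is scored.

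**The case against.** The strongest reply is that the governing criteria are already stated. Section 6.3 says imaging is assessed by irRC, 6.3.2 presents itself as the version used in this protocol, 3.5.1 points to 6.3.2, and 6.3.4 is titled as a methods section whose PET list concerns how new lesions are identified. That makes 6.3.2 the more natural reading. It does not settle the matter, because 6.3.4 assigns PD and dates it, no sentence gives precedence, and 6.3.5 and 6.3.6 are silent.

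Several stronger readings that a reader might infer are not supported:

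- *That item a is as firm as item b.* It speaks only of a sign of PD and needs a negative baseline PET, which is not scheduled.
- *That 6.3.4 declares a malignant effusion to be PD.* It makes cytology mandatory for the distinction and leaves the result implicit. The phase I patient with effusions does not help: that patient received the vaccine, and the effusions were only possibly linked to an immune response.
- *That new lesions never define progression under 6.3.2.* New measurable lesions can, through the summed burden.
- *That item c lets PET create complete responses here.* Its own condition of prospective description is unmet, so the upgrade is unavailable. CR and PR also count alike in the primary endpoint.
- *That 6.3.4 dates PD at least 4 weeks, or a 3-month scan interval, earlier.* Section 6.3.2 does not date irPD at the confirming scan, so the shift cannot be derived.
- *That the primary decision rule is undermined.* Calcitonin response is untouched. An imaging responder could be disputed only if a PET or effusion finding arose before the irPR was confirmed.

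**Conclusion.** The contradiction is real and rests mainly on FDG-PET item b. It gives PD without the 20% and 5 mm threshold and without the 4-week confirmation that 6.3.2 requires, and in one branch it back-dates PD. Item a and the cytology paragraph are softer conflicts in the same direction.

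The effect is on PFS and duration of response. PFS is a secondary objective, and section 8 specifies no analysis of it, so the weight is moderate. Each patient scored differently is 1/15 = 6.7% of a cohort. How many there would be is unknown, because the documents give no frequency of unscheduled PET, new PET-positive sites or effusions. The lesion examples rest on assumed nadir sums and otherwise unchanged disease. The calcitonin response and the operating figures in section 8 stand.

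**What to change.** 1. State at the head of 6.3.4 that it covers measurement technique only, and that PR/CR, duration of response and PFS are assigned solely by 6.3.2.
2. Reword FDG-PET items a and b so that a positive PET prompts diagnostic CT or MRI, with any new measurable lesion added to tumour burden under 6.3.2.
3. Delete item c, since its own condition is not met.
4. Reword the cytology paragraph so that a malignant new effusion is recorded as a new non-measurable lesion, and a worsening baseline effusion as non-index disease.
5. Cite irPD as defined in 6.3.2 in sections 6.3.5 and 6.3.6.
6. Reconcile 3.5.1 with the revised text.

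The cost is a text amendment, with no change to sample size and no addition to the scheduled assessments. The downside is that some true new-lesion progressions seen on PET will be dated later or not counted, which 6.3.2 already accepts by design.
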